### 7.4 Center Pooling

This is a single center study and no pooling analysis is needed.

## 7.5 Handling of Missing, Unused, and Spurious Data and Dropouts

The primary analysis will be based on all evaluable data. Handling of dropouts and missing data will depend on their frequency and the nature of the outcome measure.

Subjects who discontinue participation prematurely will be included in the analysis of results. Subjects who withdraw from the study prior to completing both regimens will be replaced by a new volunteer.

## 7.6 Adjustments for Multiple Comparisons

No multiplicity adjustments will be considered in this study.

## 7.7 Demographic and Other Baseline Characteristics

Subject demographics, medical history will be summarized using descriptive statistics for continuous variables (mean, standard deviation, number of observations, minimum and maximum) and frequency tables for discrete variables.

Baseline demographic data will be summarized and reported. This table summarizes the subject population with respect to age at entry into the study, gender. Age will be reported in years. Age will be summarized using descriptive statistics: n, arithmetic mean, standard deviation, median, and range (i.e., minimum and maximum values). Subjects with missing data that cannot be resolved prior to database lock will not be included in the tabulation and excluded from the summary statistics; gender will be summarized using counts and percentages. In addition to the reported values, unknown or unreported values will also be reported. The supportive data for the demographics table will be presented in a listing.

## 7.8 Interim Analyses

There is no interim analysis.

## 7.9 Evaluation of Objectives

The objective of this study is to investigate the relationship between BIS and propofol with/ without remifentanyl across a wide range of hypnotic states.

### Primary Objective:

To determine BIS50 (BIS value at which 50% of subjects will be unresponsive at given drug concentrations) and other dose-response parameters.

### Secondary Objective:

To determine BIS95 (BIS value at which 95% of subjects will be unresponsive at given drug concentrations) and other dose-response parameters.

The relationship between anesthetic agent concentrations and BIS responses will be modeled using the Sigmoid model (extended logistic model) as discussed previously.

The dose-response relationship by drug concentration will be presented. The estimated BIS values along with 95% confidence intervals will be provided for propofol with or without remifentanyl regimens.

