Statistics	
Data will be analyzed by Medtronic or its designee. Any changes in statistical methods will be detailed in the Clinical Study Report.
 
Standard demographic information and baseline characteristics will be summarized using descriptive statistics. For safety assessments, adverse events (AEs) will be summarized using frequency counts and percentages. Descriptive statistics will be provided by severity and relationship as needed.
 
The primary effectiveness analysis will be based on all evaluable data collected from the left side of the brain to reflect the typical operation of the device from this study. The BIS™ index value collected from the right side of the brain will be used for research.
 
Subjects who discontinue participation prematurely will be included in the analysis of results. Subjects who withdraw from the study prior to completing both regimens will be replaced by a new subject.
 
The data will be analyzed for each regimen to evaluate the dose-response relationship of the anesthetic agent concentration and BIS™ values.
 
Any subject who responds to any verbal command with MOAA/S assessment score of 2, 3, 4, and 5 will be considered as responsive. Subjects with MOAA/S assessment scores <2 will be considered unresponsive.
 
The value of BIS™ will be assessed at the different targeted-controlled drug concentrations or infusion rates. The logistic regression (simplified E_{max} model) will be used to analyze the relationship between the BIS™ index and loss of responsiveness through the probability of response curves. The values of BIS™, at which 50% (BIS₅₀) and 95% (BIS₉₅) of subjects are unresponsive, and their 95% confidential intervals will be derived. The systematic variance between groups will be evaluated. The Prediction Probability score (P_k) for correctly predicting if the subject was responsive or unresponsive will be assessed.

-------------------	--

4. Introduction

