lightness of anesthesia can result in awareness with recall of events that happen in the operation room. Too deep anesthesia could cause hemodynamic disturbances necessitating the use of vasoconstrictor agents, which constrict blood vessels to maintain normal blood pressure and cardiac output. Overly deep anesthesia can also result in respiratory depression requiring respiratory assistance postoperatively [4]. There is no objective scale that measures “too light” or “too deep” anesthesia. Bispectral Index (BIS) technology monitoring uses processed EEG signals to measure sedation depth based on level of consciousness (LOC) signals and allows anesthesia providers to titrate general anesthesia to achieve the desired LOC on the brain [4, 5]. BIS™ technology consists of a sensor, a digital signal converter, and a monitor. The sensor is placed on the patient’s forehead to pick up the electrical signals from the cerebral cortex and transfer them to the digital signal converter. BIS™ values quantify changes in the electrophysiologic state of the brain during anesthesia. Overall, a BIS™ value below 60 is associated with a low probability of response to commands. The BIS™ is a continuously processed EEG parameter that correlates to the patient’s level of hypnosis, where 100 = awake and 0 = flat-line EEG. The BIS™ parameter was designed to correlate with “hypnotic” clinical endpoints (sedation, lack of awareness, and memory) and to track changes in the effects of anesthetics on the brain. Figure 1 reflects a general association between clinical state and BIS values. Ranges are based on results from a multi-center study [5] of the BIS system involving the administration of specific anesthetic agents. BIS™ values and ranges assume that the EEG is free of artifacts that can affect its performance. Titration of anesthetics to the BIS™ range should be dependent upon the individual goals established for each patient. These goals and associated BIS™ ranges may vary over time and in the context of patient status and treatment plan.

[figure not shown]

Figure 1: BIS™ Range Guidelines; a general association between clinical state and BIS™ values

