10.5.2.4. Propofol Group

The initial target effect-site concentrations of propofol will be 0.5 µg/ml followed by incremental increases in the target effect-site concentrations of 1.5, 2, 2.5, 3, 4, 6, to a maximum of 8 µg/ml until a BIS™ value of not lower than 30 is intentionally reached or per Investigator's discretion. The BIS™ value should not intentionally be taken below 30. The equilibration time for each targeted plateau will be at least 12 minutes. The BIS™ value and MOAA/S score will be assessed and recorded when the patient is awake and at the different targeted propofol concentrations. Tetanic Electrical Stimulation (TES) will be used following the MOAA/S assessment when the subject reaches a MOAA/S score of <2. The BIS™ value will be recorded at the time of subject's response and approximately 2 minutes following the TES assessment. The propofol concentration will be decreased by the same steps until consciousness occurred.

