14.3. Statistical Methods

Standard demographic information and baseline characteristics will be summarized using descriptive statistics. For safety assessments, adverse events (AEs) will be summarized using frequency counts and percentages. Descriptive statistics will be provided by severity and relationship as needed.

Any subject who responds to any verbal command with MOAA/S assessment score of 2, 3, 4, and 5 will be considered as responsive. Subjects with MOAA/S assessment scores of <2 will be considered unresponsive. Tetanic Electrical Stimulation (TES) will be employed with an MOAA/S assessment score of <2.

The BIS^{TM} index value collected from the left side of the brain will be used for primary analysis to reflect the typical operation of the device from this study. The BIS^{TM} index value collected from the right side of the brain will be used for internal research purposes.

The value of BIS^{TM} will be assessed at the different targeted-controlled drug concentrations or infusion rates. The logistic model (simplified Sigmoid E_{max} model) will be used to analyze the relationship between the BIS^{TM} index and loss of responsiveness through the probability of response curves. The values of BIS^{TM} , at which 50% (BIS_{50}) and 95% (BIS_{95}) of subjects are unresponsive, and their 95% confidential intervals will

be derived. The systematic variance between groups will be evaluated. The Prediction Probability score (P_k) for correctly predicting if the subject was responsive or unresponsive will be assessed.

15. Ethics

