**Propofol with Remifentanil (R) regimen**

Where remifentanil is administered with propofol, approximately 2 minutes before starting propofol, to attain an effect-site targeted concentration of remifentanil of 4 ng/ml, remifentanil will be given by a continuous infusion. Approximately within 7 minutes, the infusion rate of Remifentanil may be adjusted to maintain the effect-site concentration of remifentanil of 4 ng/ml throughout the study.

The initial target effect-site concentrations of propofol will be 0.5 µg/ml followed by incremental increases in the target effect-site concentrations of 1.5, 2, 2.5, 3, 4, 6, or 8 µg/ml until MOAA/S scales at values less than 2 is reached. The propofol concentration will be decreased by the same steps until consciousness re-occurs.

The equilibration time for each targeted plateau will be at least 12 minutes. The BIS value will be recorded, and MOAA/S score will be assessed when the patient is awake and at the different targeted concentrations.

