where  $P$  is the fraction  $E/E_{max}$ . This is an extended logistic model with  $P$  as the probability of “unresponsive”. The model will be fit to the data of BIS values along with drug concentrations. The BIS values will be assessed at the different targeted-controlled drug concentrations, or infusion rates, or ET concentration at which 50% (BIS50) and 95% (BIS95) of subjects are unresponsive. The systematic variance between groups will be evaluated. The Prediction Probability score ( $P_k$ ) for correctly predicting if the subject was responsive or unresponsive will be assessed using the Smith Method.

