### 7.3 Test of Cross Over Effect

This is a cross-over study and potential carry-over effect will be assessed. Logistic regression will be used to test carry-over effect by using the regiment sequence as an indicator variable. A P-value of 0.1 or larger will be deemed as supporting the assumption of no carry-over effect. If the carry-over effect is present, further analysis will be performed by adopting appropriate statistical methods (e.g., *Laird, et al. 1992*).

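### The 95% CIs for BIS50 and BIS95 have no subject-level variance although each subject gives many readings; with default standard errors the BIS50 interval is too narrow when subjects differ materially in threshold

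*SAP*

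**What the plan says.** **Readings.** SAP 5.1 has repeated pairs in each regimen: "The BIS value will be recorded, and MOAA/S score will be assessed when the patient is awake and at the different targeted concentrations". Protocol 10.5.2.4 adds a descending limb: "The propofol concentration will be decreased by the same steps until consciousness occurred". Protocol 10.5.2.5 does the same for the remifentanil regimen, and every subject is meant to have both.

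**Models.** SAP 7.2.1 writes out one curve with a single C50 and a single gamma, and states: "The model will be fit to the data of BIS values along with drug concentrations". Protocol 14.3 applies a logistic model to the relation between the BIS "index and loss of responsiveness through the probability of response curves".

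**Intervals.** SAP 7.9 states: "The estimated BIS values along with 95% confidence intervals will be provided for propofol with or without remifentanyl regimens". The Statistics row of the Protocol synopsis promises the same for the BIS values at which 50% and 95% "of subjects are unresponsive, and their 95% confidential intervals will be derived".

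**Carry-over.** SAP 7.3: "Logistic regression will be used to test carry-over effect by using the regiment sequence as an indicator variable". A P-value of at least 0.1 is taken to support no carry-over.

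Neither document names a unit of analysis, a clustered or GEE variance, a jackknife or a bootstrap. The nearest statements do not fill the gap. The variance that SAP 7.2.1 will evaluate is between groups. The Smith method there concerns Pk only. The two-period cross-over paper in SAP 7.3 is an example for use if carry-over is found. Protocol 14 leaves the methods to the SAP.

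**The concern.** Readings from one volunteer are not separate pieces of evidence. A subject who stays responsive at low BIS values does so at several steps, on the way up and on the way down. If the written models are programmed as they stand, the software default treats each reading as an independent unit, and the standard error reflects the number of readings more than the number of people.

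BIS50 with its 95% CI is the primary result, and BIS95 is the first secondary result. An interval that is too short tells readers that the threshold is known more exactly than about 20 subjects can establish. Sequence in SAP 7.3 is a between-subject factor, so a test run on readings would not hold its 0.10 level.

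**Working it through.** **1. The plan's own figure.** Protocol 14.1 and SAP 6 give about 20 subjects, allowable error 15%, CV 25%, alpha 0.05 and power above 80%. As a one-sample calculation, n = ((z_alpha + z_beta) × CV/error)².
- One-sided: ((1.645 + 0.842) × 0.25/0.15)² = 17.2, so 18. Power at 20 is Φ(0.15/0.25 × √20 − 1.645) = Φ(1.04) = 85%.
- Two-sided: ((1.960 + 0.842) × 0.25/0.15)² = 21.8, so 22. Power at 20 is Φ(0.72) = 76.5%.

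The figure reproduces with one-sided alpha (sidedness is not stated). The formula counts one value per subject.

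**2. Readings.** Awake (1) + rising targets (8) + falling targets (7) = at most 16 per regimen, 32 per subject. Under the assumptions below the average is about 11 per regimen on the v5.0 schedule and about 6 under the SAP 5.1 rule (escalate until MOAA/S is below 2). For 20 subjects that is about 220 or 120 readings per regimen.

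**3. Direction.** Let T be a subject's threshold, with logit P(unresponsive) = (T − BIS)/s. At given BIS values, the probabilities at any two readings both rise with T, so their covariance over subjects is not negative. Default variance sets it to zero and so understates the variance of the curve's level, which drives BIS50. BIS95 also depends on the slope.

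**4. Size, v5.0 schedule.** Only the 20 subjects and the target steps come from the documents. Assumed: T normal, mean 65, SD = CV × 65 (3.25 at 5%, 6.5 at 10%); s = 3 or 6 BIS units; BIS from a subject Hill curve (baseline 95, maximum fall 75, exponent 2, median C50 2.7, log-SD 0.25, noise SD 4). As a simulation device only, ascent ends at BIS 40 or less or at the top target. There were 2,000 trials per scenario, with the Protocol 14.3 model. Coverage is scored against the pooled fit's large-sample value, so it measures width, not bias. The hand check is 2Φ(1.96/ratio) − 1.

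| Threshold CV | True SD / default SE, s = 3 | s = 6 | Hand check | Simulated BIS50 coverage |
|---|---|---|---|---|
| 0% | 0.86/0.85 = 1.01 | 1.35/1.31 = 1.03 | 94-95% | 95% |
| 5% | 1.16/0.94 = 1.23 | 1.50/1.35 = 1.11 | 89-92% | 88-92% |
| 10% | 1.74/1.14 = 1.53 | 2.03/1.45 = 1.40 | 80-84% | 80-84% |
| 25% | 3.98/1.82 = 2.19 | 4.15/2.02 = 2.05 | 63-66% | 63-67% |

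Ending ascent at BIS 35 or 45 (s = 3) gives 88.2% or 88.5% at CV 5%, and 78.0% or 79.0% at CV 10%. A second simulation (800 trials, ascent to near BIS 30, s = 3) gives 94.4%, 92.9%, 91.1% and 81.1% at threshold SDs of 0, 1, 3 and 6 BIS units.

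**5. Size, SAP stop rule.** The second simulation gives 93.1%, 92.9%, 91.2% and 86.0% at the same SDs, and 89.5% at SD 6 with s = 5. Over all runs the range is about 90-93% at CV 5% and 86-91% at CV 10%. At SD 1 the SD/SE ratio is 1.03-1.05 over both schedules, inside the 1.00-1.06 seen with no heterogeneity.

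**6. Plausible spread.** Protocol 4.1.2 says that a BIS "value below 60 is associated with a low probability of response to commands". With mean 65, the share of thresholds below 60 is Φ(−5/3.25) = 6%, Φ(−5/6.5) = 22% and Φ(−5/16.25) = 38% at CV 5%, 10% and 25%. The 25% row is therefore only an upper bound. With mean 70 and CV 10% the share is Φ(−10/7) = 8%, and coverage is still 77-82%.

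**7. BIS95 and C50.** Default BIS95 coverage (v5.0) is 94%, 90-94% and 88-91% at CV 0, 5 and 10%. For the SAP 7.2.1 curve, a pooled logistic fit on log concentration (1,000 trials, similar assumptions) gives default C50 coverage of 75-83% (v5.0) and 87-89% (SAP rule). With identical BIS thresholds it is still 80-82% and 88%, because subjects differ in drug sensitivity.

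**8. Carry-over test.** Assumed: 10 subjects per sequence, both regimens pooled, v5.0 schedule, no true carry-over. With BIS and regimen as covariates, the default false-signal rate at 0.10 is 10-11%, 16-27% and 30-41% at CV 0, 5 and 10%. With BIS left out it is 2-3%, 3-5% and 9-12%. Clustered by subject it is 8-12% under both.

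**9. Subject-level variance.** On the v5.0 schedule, clustering with t(19) gives 94-96% for BIS50 and 91-94% for BIS95. The jackknife gives 94-96% and 92-95%. Under the SAP rule, clustered BIS50 coverage is about 90-94%. BIS95 there is 88-92% in the second simulation, no better than the default 88-92%.

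**The case against.** The strongest reply is that the plan is silent, not wrong. A reader might infer that it adopts independence. No passage does, and a competent analyst could cluster by subject without contradicting a word of it. That stands, and every coverage figure is conditional on default standard errors. It does not make the gap harmless: the SAP writes out single-curve formulas, promises intervals, and presents itself as the detailed account of methods.

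A reader might also infer that the models are wrong for lack of a subject term. The documents do not support this. BIS50 is defined by the share of subjects unresponsive, which reads as a population-average target, and a pooled curve can estimate it. Only the variance is at issue.

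The sizes are open to challenge. The documents give no between-subject threshold SD, and the BIS50 and BIS95 figures belong to the Protocol 14.3 model. The escalation rules also differ: SAP 5.1 stops on MOAA/S, while Protocol v5.0 refers to a BIS value or discretion. Those passages need reconciling separately, and nothing here prefers either. The shortfall is smaller under the SAP rule, which is why both are shown.

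The carry-over rates are the weakest part. SAP 7.3 gives no outcome, covariates or unit, the two assumed models err in opposite directions at small CV, and a subject-level test is not excluded.

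**Conclusion.** The concern holds in conditional form and should be fixed before analysis. The plan promises 95% CIs for its primary and first secondary results from pooled repeated readings, with no subject-level variance. With default standard errors, the BIS50 interval is too narrow when thresholds differ materially between subjects, and the C50 interval is too narrow when drug sensitivity differs.

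The direction follows from the design; the size rests on assumed thresholds. At CV 5-10%, coverage falls a few points to about 17 points short of 95% on the v5.0 schedule (95 − 78 = 17), and up to about 9 points short under the SAP rule (95 − 86 = 9). At an SD of about 1 BIS unit the shortfall is negligible.

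Two stronger conclusions are not supported. Coverage near 65% should not be expected, because a CV of 25% fits poorly with Protocol 4.1.2. Nor would a wrong trial decision follow, because no success criterion depends on the interval. For SAP 7.3, the sound statement is that a reading-level test does not hold its 0.10 level; direction and size depend on a model that the SAP does not state.

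**What to change.** In SAP 7.2.1 and 7.9, state that the subject is the independent unit. Compute the CIs of BIS50, BIS95 and C50 with a subject-clustered (sandwich/GEE) variance, a named small-sample correction and a t reference on subjects minus 1, or with a delete-one-subject jackknife. In SAP 7.3, state the outcome and covariates, and test the sequence term with the same subject-level variance. No subject term in the mean model is needed, and Protocol 14.3 can refer to the SAP.

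The cost is a few sentences and a few lines of code, with no change to design or data collection. Intervals widen on the v5.0 schedule: BIS50 by about 1.06 times with no heterogeneity, 1.2-1.3 times at CV 5% and 1.5-1.6 times at CV 10%; BIS95 by about 1.05, 1.07 and 1.1-1.2 times. With 20 subjects the repair is not complete. Clustered coverage can stay slightly low for BIS95 and under the SAP stop rule, and BIS95 under that rule may gain little. The report should say so beside the interval.

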## 7.10 Safety Evaluation

Safety evaluation will be based on all enrolled subjects in this study. Adverse events will be summarized using frequency counts and percentages. Descriptive statistics will be provided by event type, severity, and relationship to study procedures and devices.

Unanticipated device effect (UADE), Serious Adverse Device Effect (SADE) and Unanticipated Serious Adverse Device Effect (USADE) will also be summarized by frequency table. Individual listings of adverse events, including event type, start date, duration, severity, and device-relatedness, will be provided as appropriate.

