Study Design	This is a single-center, prospective, non-randomized, cross-over study to collect data to evaluate the relationship between BIS™ and anesthetic regimens. The subjects will receive two regimens of anesthesia with different drug combinations, with at least a 1-week washout period between regimens. Subjects will be sequentially assigned to start with either Propofol (P) or Propofol with 4 ng/ml of Remifentanyl (R) regimens with the BIS™ bilateral sensor placed on the subject's forehead. The Modified Observer's Assessment of Alertness/Sedation (MOAA/S) scale will be used to measure the level of alertness in sedated subjects, with Tetanic Electrical Stimulation (TES) being used once the patient is unresponsive to tactile stimuli (e.g., MOAA/S < 2). The loss of tactile stimulus response will be defined according to the MOAA/S score value <2.

Medtronic Controlled Information

Clinical Investigation Plan

[figure not shown]
SONORA

MDT19049SONORA

Version 5.0

Page 11 of 75

Medtronic

	
TES will then be initiated once the subject reaches an MOAA/S <2, with a one-time stimulation of 50mA, 50 Hz delivered for 5 seconds. The subject's response will be recorded along with the BIS™ value prior to stimulation, at the time of stimulation and 2 minutes following stimulation. The data will be used to gauge the influence of stimulation on the subject's level of sedation, pre-TES and post-TES.
 
Sample Size	
To collect 20 complete data sets, up to 30 subjects will be enrolled to account for anticipated screen failures and subject dropouts. Based on the dose-response Hill equation with an allowable error of $\pm 15\%$ for BIS₅₀ and coefficient of variation of 25% at the alpha level of 0.05, the sample size will provide sufficient power (>80%) to evaluate the performance of anesthetic agents/ regimens.

Duration	
The study duration is expected to be up to approximately 4 months. The expected duration of each subject will be approximately (~) 10 hours. The Enrollment Visit should take approximately 2 hours to complete, and each Study Visit will be approximately 4 hours per subject. Each subject will be contacted by phone within 48 hours of the study participation.

Planned number of sites	
1 site in the US

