9.2. Subject Enrollment

Subjects will be enrolled in the study once all eligibility requirements for the study have been met. Subjects who give informed consent for the protocol in order to undergo screening for eligibility are not considered enrolled and should not be enrolled until the screening is completed as indicated in *Sections*

8.3, 8.4, and 9, and they are determined to meet all eligibility criteria. Study enrollment is accomplished by signing of the informed consent and successfully passing the study inclusion /exclusion criteria and health screening evaluation. Subjects who sign informed consent, but are not enrolled, are considered screen failures.

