- Adverse event review will be completed to assess events the baseline, and that occur after enrollment.

The **Baseline/ Enrollment** results will stay valid for **60 days**.

10.5. Execution – Visit 2

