10.8. Assessment of Safety

For safety analyses, adverse events will be summarized using frequency counts and percentages, refer to *Section 14*. Descriptive statistics will be provided by event type, severity, and relationship to study

procedures and devices. Individual listings of adverse events, including event type, start date, duration, severity, and device-relatedness, will be provided as appropriate. Adverse events occurring during the procedure or 48 hours after the procedure will be recorded. For AEs and AE reporting requirements, refer to *Section 11*.

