12.1. Adverse Events

AE (Adverse Event) definitions are provided in **Table 4**. AE information will be collected throughout the study from the BIS™ sensor application until the follow-up phone call. A list of anticipated adverse events and risks that are expected in nature is included in *Section 10*.

Reporting of these events to Medtronic will occur on an AE Form. Each event must be reported separately. Documented pre-existing conditions are not considered AEs unless the nature or severity of the condition has worsened.

For AEs that require immediate reporting (see **Table 4**), initial reporting may be done by phone, fax, or on the eCRF completing as much information as possible. The completed AE eCRF must be submitted to Medtronic as soon as possible.

Any medication/treatment associated with the treatment of an AE must be reported

AE assessment for the purposes of this study will cease after the follow-up phone call within 48 hours after the procedure. All AEs considered at least possibly related to the study will be followed until resolved, stabilized, and/or returned to baseline.

Table 4: Definition of Adverse Events and Device Deficiencies

General	
Adverse Event (AE)	Any untoward medical occurrence, unintended disease or injury, or untoward clinical signs (including abnormal laboratory findings) in subjects, users or other persons, whether or not related to the investigational medical device. NOTE 1: This definition includes events related to the investigational medical device or the comparator.

Clinical Investigation Plan

SONORA

MDT19049SONORA

Version 5.0

Page 51 of 75

Medtronic

	
NOTE 2: This definition includes events related to the procedures involved.
 
NOTE 3: For users or other persons, this definition is restricted to events related to investigational medical devices.

Adverse Device Effect (ADE)	
Adverse event related to the use of an investigational medical device.
 
NOTE 1: This definition includes adverse events resulting from insufficient or inadequate instructions for use, deployment, implantation, installation, or operation, or any malfunction of the investigational medical device.
 
NOTE 2: This definition includes any event resulting from use error or from intentional misuse of the investigational medical device.

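### AE percentages rest on all enrolled rather than exposed subjects, no AE table is split by regimen, and the AE window is defined inconsistently

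*SAP*

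**What the plan says.** **Base and breakdown.** SAP 7.10 states: "Safety evaluation will be based on all enrolled subjects in this study". AEs are given as counts and percentages, and "Descriptive statistics will be provided by event type, severity, and relationship to study procedures and devices". Neither regimen nor period is named as a breakdown there, in Protocol 10.8 or in Protocol 14.3. SAP 7.1.3 defines an evaluable set and a per-protocol set, but none based on exposure.

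**Who is enrolled.** The Protocol gives three accounts.
- Section 9.2: "Study enrollment is accomplished by signing of the informed consent and successfully passing the study inclusion" and exclusion criteria and the health screen. Screen failures are not enrolled.
- Section 10.5.1, on the day of Visit 2: enrolment rests on eligibility checks at Visits 1 and 2.
- Synopsis, Sample Size: "To collect 20 complete data sets, up to 30 subjects will be enrolled", with the margin covering screen failures as well as dropouts. Section 14.1 agrees.

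**AE window.**
- Start: Section 12.1 collects AEs from BIS "sensor application until the follow-up phone call", and the Synopsis (Safety) agrees. Section 10.4, under Visit 1, says: "Adverse event review will be completed to assess events the baseline, and that occur after enrollment". Protocol Table 2 and SAP Table 1 both mark AE assessment at Visit 1 and again before the procedure.
- End: Section 10.8 says: "Adverse events occurring during the procedure or 48 hours after the procedure will be recorded". Section 12.1 says: "AE assessment for the purposes of this study will cease after the follow-up phone call within 48 hours after the procedure". Section 10.6.1 sets a latest time for the call but no earliest time.

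**The concern.** There are three separate defects; none follows from another.

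First, a percentage that describes the safety of a device or drug regimen should have as its denominator the people who received it. With all enrolled subjects as the base, anyone who drops out between enrolment and sensor application counts as a subject without an exposure-related event.

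Second, the two regimens differ by an opioid, and the Protocol itself expects that to matter: Table 3 notes that reduced cardiac output under propofol is more frequent with concurrent opioid use. Protocol 6.2 nevertheless states that the chosen remifentanil target carries no added AE risk. No planned table would show whether the data bear that out. Relatedness does not help, because Table 5 classifies it to device or procedure, not to regimen.

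Third, with two start points and two end points, it is unclear which events belong in the tables, and the time observed can differ between subjects.

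Protocol 6.2 gives confirming the safety of BIS as part of the rationale, and Section 13 provides no data monitoring committee. The tables in SAP 7.10 are therefore the planned safety summary.

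**Working it through.** The plan states no AE rate and no safety precision, so there is no figure of its own to reproduce here. The number never exposed, the AE rate and the call times are not given either; the values below are assumptions that show a range.

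**1. Denominator.** Inputs: up to 30 enrolled and 20 complete data sets (Synopsis, Sample Size). If every recorded AE occurs in an exposed subject,

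reported % ÷ % among exposed = exposed ÷ enrolled.

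With 30 enrolled and, for illustration, 5 subjects with an AE:

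| Exposed | Exposed ÷ enrolled | Reported (5/30) | Among exposed |
|---|---|---|---|
| 30 | 1.00 | 16.7% | 5/30 = 16.7% |
| 28 | 0.93 | 16.7% | 5/28 = 17.9% |
| 25 | 0.83 | 16.7% | 5/25 = 20.0% |
| 20 | 0.67 | 16.7% | 5/20 = 25.0% |

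The last row is the extreme: it treats everyone beyond the 20 complete data sets as never exposed. Under 9.2, screen failures are outside the count, so only losses between enrolment and sensor application dilute it. Under 10.5.1, if enrolment is completed by the Visit 2 checks, that number is close to zero. It could be larger if enrolment is fixed at Visit 1, because Visit 1 results stay valid for 60 days (10.4) and drug, alcohol and pregnancy tests follow on the procedure day (10.5.1).

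**2. Regimen.** Suppose 20 subjects receive both regimens and no subject has an AE under both. With 2 subjects affected under one regimen and 8 under the other, the regimen percentages are 2/20 = 10% and 8/20 = 40%. With 5 and 5 they are 25% and 25%. The pooled table shows 10/20 = 50% either way. Numbers exposed can also differ by regimen, because subjects who withdraw before completing both are kept in the analysis and replaced (Protocol 14.2, SAP 7.1.3).

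**3. End of the window.** Hours covered = call time ÷ 48.

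| Call at | Share of the 48 hours covered |
|---|---|
| 6 h | 12.5% |
| 12 h | 25% |
| 24 h | 50% |
| 36 h | 75% |
| 48 h | 100% |

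These are shares of time; they are shares of events only if onset is uniform over the 48 hours. After the first regimen, the Synopsis lists an AE assessment before the procedure at Visit 3, which can pick up events after the first call. After the second regimen only the call remains.

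**4. Start of the window.** Under 12.1 and the Synopsis, an enrolled subject who never has a sensor applied cannot contribute an AE. Under 10.4, Table 2 and SAP Table 1, that subject can. The choice of start date therefore decides whether an all-enrolled base matches the events counted.

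**The case against.** A reader might infer that the plan understates AE rates. The documents do not show that. Screen failures are not enrolled under 9.2, and 10.5.1 ties enrolment to the Visit 2 checks, so enrolled and exposed may nearly coincide. Anyone who leaves after starting Visit 2 has been exposed and belongs in either denominator, so 20 exposed out of 30 has no support beyond being arithmetically possible. This objection stands: dilution is possible but not demonstrated.

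A reader might also infer that AEs are collected only from sensor application. That takes one side of a contradiction. If collection starts at Visit 1, an all-enrolled base fits the collection period, although it still mixes events before and after exposure.

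Nor can an average loss of follow-up be claimed. Call times are not given, and 10.6.1 asks about problems since discharge, so a call at hour zero is not realistic. Some expected reactions are brief: the Protocol describes sensor irritation as usually resolving within hours (11.1.1.1). That limits the likely loss but does not reconcile 10.8 with 12.1.

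On regimen, the objectives are BIS50, BIS95 and Pk, the safety rationale concerns the BIS device, and the study is small and descriptive. SAP 7.10 plans AE listings with start dates, and the regimens are at least a week apart, so the regimen at onset can usually be recovered by hand. It would be too strong to say that a difference is hidden. What remains is that the planned summary does not show it, and that hand reconstruction from listings supplies no regimen-specific denominators.

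**Conclusion.** The point holds as three separate defects: a safety base of enrolled rather than exposed subjects, no AE summary by regimen in a two-regimen crossover, and an AE window that conflicts on both start and end. The missing regimen split and the conflicting window can be read directly from the text and need no numerical assumption.

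The effect on percentages is conditional. It ranges from none, if every enrolled subject is exposed, to a reported figure one third too low, if only 20 of 30 are exposed and all AEs occur in exposed subjects. The documents do not place the study within that range, and 10.5.1 points to the lower end. The loss from an early call is also unquantified and falls mainly after the second regimen.

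The primary and secondary effectiveness analyses are unaffected. This is an inexpensive improvement to the safety reporting.

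**What to change.** In SAP 7.10 and SAP 7.1.3:
- Define the safety set as subjects with a BIS sensor applied or any study infusion started. Keep all enrolled subjects for disposition.
- Tabulate AEs by regimen at onset, with the number exposed to that regimen as denominator. State how an event between the two procedures is assigned.
- List any AEs before exposure separately.

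In the Protocol, reconcile the Synopsis (Safety), Table 2, 10.4, 10.8 and 12.1 so that one AE window applies, with one start and one end, and bring 10.6.1 and SAP Table 1 into line. Say also which account of enrolment applies (9.2, 10.5.1 or the sample-size text).

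Report the time of each follow-up call, so that subjects contacted before the stated window closed can be identified. Section 10.6.1 already requires each call attempt to be documented at the site; the contact time needs to reach the analysis data.

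The cost is wording in both documents and one extra table split. Apart from carrying over the call time, it uses data already collected. AE percentages may become slightly less favourable.
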